8. RESEARCH METHODOLOGY DESCRIPTION

Study type: Observational, cross-sectional study

Data collection:

Patient data will be collected from the hemodialysis department of Tartu University Hospital. All participating patients will undergo BIA. BIA analysis will be performed using dialysis-related measurement instruments, as described in the methodology section. This will be done before routine dialysis and does not require a separate visit. The patient does not need to come in specifically for this purpose.

The following data will be collected from participating patients:

Demographic data:

- Age
- Gender
- Height
- Weight
- Body mass index (BMI)
- Duration of dialysis (months/years)

Bioelectrical impedance analysis (BIA):

- Fat mass
- Fat-free mass

- Total body water
- Extracellular water
- Phase angle

Laboratory parameters:

- eGFR

Bioelectrical impedance measures body fat, muscle, and water using a low-voltage electric current that is harmless and imperceptible to the patient. Two electrodes are placed on the wrist and two on the ankle, similar to an EKG but faster (approximately 5 minutes). Although the procedure is safe, it requires minimal patient preparation. Measurements will only be taken from patients who consent. Measurements include fat mass, fat-free mass, total body water, extracellular water, and phase angle. To minimize fluid shifts, measurements will be taken before dialysis. eGFR will be taken from the patient's recent blood test. eGFR data will be collected routinely and will use measurements from the last 6 months. Clinical data such as dialysis duration and comorbidities will also be considered.

Data analysis will be performed using statistical software (SPSS).

The analysis will include several steps to thoroughly evaluate the relationship between bioelectrical impedance analysis (BIA) parameters and estimated glomerular filtration rate (eGFR) in hemodialysis patients. Descriptive statistics will summarize the main characteristics, such as age, gender, dialysis duration, eGFR, and BIA parameters. Pearson or Spearman correlation tests will be used to assess relationships between BIA measurements (e.g., fat mass, lean body mass, phase angle) and eGFR. Multivariate regression analysis will identify significant predictors of malnutrition and clinical outcomes, focusing on factors such as phase angle, lean body mass, and fluid status.

Data will be collected from the hemodialysis department of Tartu University Hospital.

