5. OBJECTIVE, SUMMARY, AND RATIONALE OF THE PROPOSED RESEARCH

The primary objective of the study is to assess the correlation between BIA-derived body composition parameters (e.g., fat mass, fat-free mass, total body water, phase angle) and eGFR in hemodialysis patients.

The study will investigate how BIA and eGFR can be used together to more effectively monitor nutritional interventions in hemodialysis patients. The study will also assess the prevalence of malnutrition and protein-energy wasting (PEW) in the study population using BIA and eGFR data.

Hemodialysis patients often suffer from complex nutritional problems due to the interplay between kidney function, protein-energy wasting, and fluid management. Current nutritional assessments in hemodialysis patients are limited, with most relying on clinical observations or basic biochemical tests. A more comprehensive, non-invasive approach is needed to assess both nutritional status and fluid balance. The study will determine whether comparing BIA metrics with eGFR provides a better picture of the patient's nutritional and kidney health, which could improve patient outcomes and dialysis management.

Malnutrition, fluid balance disorders, and protein-energy wasting (PEW) are common in hemodialysis patients due to the effects of chronic kidney disease (CKD) and dialysis therapy. Nutritional status is a critical factor influencing patient outcomes but is often under-monitored.

Traditional methods of assessing kidney function, such as estimated glomerular filtration rate (eGFR), provide an overview of kidney health but do not directly measure body composition or nutritional value. In contrast, bioelectrical impedance analysis (BIA) provides detailed information on body composition, including fat mass, fat-free mass, total body water, and phase angle. The aim

of this study is to investigate the relationship between BIA-derived nutritional markers and eGFR to assess their combined utility in evaluating the nutritional status of hemodialysis patients.

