7. INCLUSION AND EXCLUSION CRITERIA

Sample size: 25-30 adult hemodialysis patients will be recruited.

Inclusion criteria:

- Patients must be 18 years or older.
- Patients must have been receiving regular hemodialysis for at least the last 6 months.

Exclusion criteria:

- Patients with a pacemaker or implanted defibrillator will not be included, as these are contraindications for BIA.
- Pregnant women will not be included due to changes in body composition and safety concerns.
- Patients who have recently had an acute illness or surgery that affected their hydration or nutritional status, as this could provide inaccurate body composition results.

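### Pre-dialysis BIA at an unfixed interval carries retained fluid into the body water and fat-free mass correlations with eGFR; the likely distortion is modest, and intracellular water would check it

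*Protocol*

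**What the plan says.** Section 8 places BIA before a routine session: "This will be done before routine dialysis and does not require a separate visit". The reason follows later in the section: "To minimize fluid shifts, measurements will be taken before dialysis". No session of the week and no interval since the last dialysis is named. Neither the interval nor fluid gain is in the list of data to collect.

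The outputs are listed: "Measurements include fat mass, fat-free mass, total body water, extracellular water, and phase angle". Section 5 states the main aim: "The primary objective of the study is to assess the correlation between BIA-derived body composition parameters" and eGFR. It treats the outputs as nutritional, since the study is to "investigate the relationship between BIA-derived nutritional markers and eGFR to assess their combined utility in evaluating the nutritional status of hemodialysis patients". The planned analysis is a Pearson or Spearman correlation of BIA measurements with eGFR, and no account of fluid is stated for it. Fluid status appears in a separate multivariate regression for malnutrition and clinical outcomes, "focusing on factors such as phase angle, lean body mass, and fluid status".

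Two other statements bear on the point. Section 5 says: "Malnutrition, fluid balance disorders, and protein-energy wasting (PEW) are common in hemodialysis patients". Section 7 excludes recent acute illness or surgery that "affected their hydration or nutritional status, as this could provide inaccurate body composition results".

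**The concern.** Fluid builds up between sessions and is removed by dialysis. A pre-dialysis reading therefore includes whatever has accumulated, and the amount depends on the length of the gap and on remaining urine output. Where fat-free mass is derived from body water, retained water is read as lean tissue.

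Fluid that varies at random only adds noise. Fluid that varies with residual kidney function is more troublesome, because eGFR is the other variable in the primary correlation. Patients with lower eGFR could then show higher TBW and fat-free mass from water alone, and the report could present this as a link between nutrition and kidney function. Section 7 shows that the protocol already regards disturbed hydration as a source of error in body composition.

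**Working it through.** The protocol gives no figure to reproduce: n = 25-30 is stated without a target correlation, SD or power. What follows is an illustration. Only n comes from the protocol (section 7); every other input is an assumption.

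**Assumed inputs.** Gain of 1 L (1 kg) per day; gaps of 2 or 3 days, equally likely; gain falling by a fraction s = 0.2 to 0.4 per SD of eGFR; TBW before fluid gain with SD 4, 5 or 6 L and unrelated to eGFR; retained fluid wholly extracellular; fat-free mass = TBW/0.73.

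**1. Effect on a single reading.** 2 L reads as 2/0.73 = 2.74 kg of fat-free mass and 2 - 2.74 = -0.74 kg of fat. 3 L reads as 4.11 kg and -1.11 kg.

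**2. Spurious correlation of TBW with eGFR.** Let g be standardised eGFR and retained fluid w = gap × (1 - s·g). The mean gap is 2.5 and the mean squared gap is (4 + 9)/2 = 6.5.
- Cov(w, g) = -2.5s, which is -0.5 or -1.0.
- Var(w) = 6.5(1 + s²) - 2.5², which is 0.51 or 1.29.
- r = -2.5s / √(SD² + Var(w)).

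For SD = 5 and s = 0.4: r = -1.0/√(25 + 1.29) = -0.195. Fat-free mass = TBW/0.73 is a rescaling of TBW, so its r is the same.

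**3. How often this reaches p < 0.05 at n = 30.** The Fisher approximation is Φ(√27·atanh|r| - 1.96) + Φ(-√27·atanh|r| - 1.96). For r = -0.195: √27 × 0.1975 = 1.026, giving Φ(-0.934) + Φ(-2.986) = 0.177.

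| TBW SD | s = 0.2: r (rate) | s = 0.4: r (rate) |
|---|---|---|
| 4 L | -0.123 (10%) | -0.240 (25%) |
| 5 L | -0.099 (8%) | -0.195 (18%) |
| 6 L | -0.083 (7%) | -0.164 (14%) |

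Simulation at n = 30 under inputs of this kind gives about 7-22%, in line with the table apart from its most extreme cell. With s = 0, r is 0 and the rate is the nominal 5%. For scale, |r| must exceed about 0.36 at n = 30, or 0.40 at n = 25, to be significant.

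**4. Intracellular water.** If true values are T and E, measured TBW - ECW = (T + w) - (E + w) = T - E. The retained fluid cancels, and the simulated false-positive rate stays near 5%.

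**5. Fixing the gap at d days.** Now r = -s·d/√(SD² + s²d²). With SD 5 and s = 0.4, d = 2 gives -0.8/√25.64 = -0.158 and d = 3 gives -1.2/√26.44 = -0.233, against -0.195 for mixed gaps. Between-session variation goes, but the eGFR-related part changes little, and it falls only if the common gap is the shorter one.

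**6. Adjusting for ECW/TBW.** The ratio depends on retained fluid and also on body size. Take a starting ratio of 0.457 and add 2.5 L. At TBW 30 L it becomes (13.71 + 2.5)/32.5 = 0.499; at 40 L, (18.28 + 2.5)/42.5 = 0.489. The ratio is thus a common effect of eGFR (through fluid) and of lean tissue, and conditioning on it links the two. In simulation, adjusting TBW-based fat-free mass for the ratio raised the false-positive rate from about 7-22% to about 10-32%.

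**The case against.** The best reply is that the stated reason is sound in its ordinary sense: measuring before dialysis avoids shifts during and just after the session. That stands. A reader might infer that the reason is false, or that section 8 contradicts the exclusion in section 7. The text supports neither reading. The protocol does not claim normal hydration, and the exclusion concerns acute illness or surgery. The exclusion shows only that the authors accept hydration as a source of error.

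A reader might also infer a large bias from ECW or ECW/TBW. Under similar assumptions those gave mean r of -0.19 to -0.35 and -0.28 to -0.49, with significance in 17-49% and 34-84% of samples. But they are fluid measures, so their correlation with eGFR would be a real fluid relation and not a false nutritional one. The ratio is not a planned measure either.

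It would be too strong to say that fluid is ignored. Section 8 names fluid status in the regression, section 5 wants fluid balance assessed as well as nutrition, and derived variables may be defined in an SAP that is not shown. The regression does not protect the primary correlations, however, and the measurement timing and the list of data are protocol matters.

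Three further limits stand. That any session may be used is inferred from silence. The device model is not named, and one that separates excess fluid would reduce the effect on fat-free mass. The date of data collection is kept in the code key (section 9), so the gap might be reconstructed from dialysis records until the planned deletion.

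**Conclusion.** The point holds in a limited form. Pre-dialysis timing is defensible, but the readings are in a fluid-loaded state at an interval that is neither fixed nor listed for collection, and raw TBW and fat-free mass are then read as nutritional markers.

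The size is modest for TBW and for fat-free mass read as TBW/0.73: mean spurious r of about -0.1 to -0.2 and a false-positive rate of about 7-22% at n = 30. This rests entirely on assumed gain, gaps, SDs and hydration constant, and above all on gain being larger when eGFR is lower. Without that dependence the spurious correlation vanishes. Correlations of phase angle and fat mass with eGFR were not quantified, so no claim is made about their size. This is a cheap improvement to measurement and interpretation; the primary analysis is not invalid because of it.

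**What to change.** 1. Keep the pre-dialysis measurement with no extra visit. Take every patient's BIA after the same interdialytic gap within the existing schedule, and add the gap to the data collected. This removes variation between sessions but does little to the eGFR-related part.
2. From data already collected, derive intracellular water = TBW - ECW. Report its correlation with eGFR as the lean-tissue measure beside the planned correlations, and treat TBW, ECW and ECW/TBW as fluid measures.
3. Reword the rationale in section 8 to say that pre-dialysis timing avoids shifts around the session and that values are in the fluid-loaded state. State that a TBW or fat-free mass correlation with eGFR will not be read as nutritional unless intracellular water shows it too.
4. Do not adjust fat-free mass for ECW/TBW.

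The cost is some protocol wording, one recorded item, one derived variable and slightly less flexible scheduling in the February-March 2025 collection period. The intracellular water figure is only as good as the device's separation of ECW from TBW.

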3. RESEARCH FUNDING

The only research to be conducted specifically for this study is the BIA analysis. This will be carried out by the researcher using equipment belonging to the University of Tartu (UT), for which no additional fee will be charged. The equipment used includes a bioelectrical impedance analysis device, which is already available and in use in the nephrology department. All other reviewed tests are those that have already been performed for clinical reasons and registered in the patients' hospital records in the eHL system.

The study (comparative analysis of bioelectrical impedance analysis (BIA) and estimated glomerular filtration rate (eGFR) for assessing nutritional status in hemodialysis patients) does not have an external funding source. This study will be conducted in compliance with ethical research standards. All aspects of the study, including data collection, analysis, and reporting, will be carried out without external financial support.

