6. RESEARCH TIMELINE

Data collection: February – March 2025

Data analysis: April 2025

Report writing, completion, and presentation: April – June 2025

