9. ANALYSIS OF ETHICAL ASPECTS OF THE RESEARCH

Confidentiality and data protection are paramount in this study. To ensure privacy, the consent form will not include contact details, birthdates, or personal identification codes. Personal data will be processed in accordance with the University of Tartu Hospital's established procedures, following the requirements of the Personal Data Protection Act.

Collected personal data will be coded, and only coded data will be processed and analyzed. All personal data will be securely stored in a folder on the University of Tartu's OneDrive server, accessible only to authorized researchers. This folder is protected by the University of Tartu's secure password system and can only be accessed by authorized users. The link between the data collected during the study and the patient's identity will only be known to the researcher conducting the analysis and those with access to the code key.

The code key will contain the following information: patient name, study ID, personal identification code, phone number, and data collection date. This code key will be deleted one year after the study's follow-up period, at which point the data will be fully anonymized. Anonymization is planned for April 2026, and anonymized data will be stored in a password-protected folder on the University of Tartu's OneDrive server.

Pseudonymized data (i.e., coded study data) will remain accessible only to the researchers involved in the study until the code key is deleted. Copies of consent forms will be securely stored in a locked cabinet in the University of Tartu Hospital's locked office, located in room L6027 on the 6th floor of building L. These consent forms will be stored until June 2032.

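### The planned regression on clinical outcomes cannot be delivered by a cross-sectional study that names no outcome and describes no follow-up

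*Protocol*

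**What the plan says.** The analysis paragraph of Protocol section 8 (Research methodology description) ends with a regression: "Multivariate regression analysis will identify significant predictors of malnutrition and clinical outcomes". It is to focus on phase angle, lean body mass and fluid status.

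The same section sets the design: "Study type: Observational, cross-sectional study". On the BIA reading it says "This will be done before routine dialysis and does not require a separate visit", and on its content "Measurements include fat mass, fat-free mass, total body water, extracellular water, and phase angle". The only laboratory item is eGFR: "eGFR data will be collected routinely and will use measurements from the last 6 months". The section adds that clinical data will be taken into account, with time on dialysis and comorbidities as examples.

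Section 6 (Research timeline) gives "Data collection: February – March 2025" and puts data analysis in April 2025. Section 9 (Analysis of ethical aspects) states "This code key will be deleted one year after the study's follow-up period" and plans anonymization for April 2026.

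**The concern.** A regression that identifies predictors of clinical outcomes needs an outcome variable. If the word predictor is to carry prognostic meaning, it also needs the outcome to come after the measurement. The protocol supplies neither.

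An analyst who follows the sentence has two ways to go. One is to find no outcome and fit no model. The other is to choose something at the analysis stage, call it an outcome, and report phase angle or lean mass as predicting it. The second is the harmful one. Section 5 hopes that the work could improve patient outcomes and dialysis management, and a reported predictor of clinical outcomes would appear to give that hope prognostic support which these data cannot provide.

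This is not a detail that a protocol would leave to a statistical analysis plan. A plan can specify the model, but it cannot supply an outcome that the study does not collect.

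**Working it through.** The protocol gives no figure to reproduce here. The check compares the analysis target with the data items and the dates.

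**Step 1: data items against the regression target (section 8).**

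| Group | Items | Count | Named as a clinical outcome |
|---|---|---|---|
| Demographic | age, gender, height, weight, BMI, time on dialysis | 6 | 0 |
| BIA | fat mass, fat-free mass, total body water, extracellular water, phase angle | 5 | 0 |
| Laboratory | eGFR | 1 | 0 |
| **Total listed** | | **6 + 5 + 1 = 12** | **0** |

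Outside the list, comorbidities are to be considered as clinical data. Recorded at one time point they are patient characteristics, and the protocol does not call them outcomes. Death, hospital admission, complications and change over time do not appear among the data items.

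**Step 2: timeline (section 6).** Collection covers February and March 2025, which is 28 + 31 = 59 days. Analysis is in the next month. No second contact, later record review or other observation after the BIA reading is described.

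**Step 3: the follow-up period in section 9.** This is the only text that could suggest later observation. The code key is deleted one year after that period, at which point the data become anonymous, and this is planned for April 2026. April 2026 minus one year is April 2025. The period therefore ends at about the close of data collection and the start of analysis, so it adds no observation time.

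**Step 4: what follows.** With no outcome named, collected or observed, the clinical-outcomes half of the regression has no dependent variable. If one were found during analysis, the protocol would not establish whether it came before or after the BIA reading. A fitted coefficient could then be described as an association at most, and not as a prediction.

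**Step 5: what is not affected.** Section 5 sets out the primary objective (correlation of BIA parameters with eGFR), the joint use of the two for monitoring nutritional interventions, and the prevalence of malnutrition and protein-energy wasting. Prediction of clinical outcomes is not among these objectives. The malnutrition half of the regression can be run as a cross-sectional analysis as far as this point is concerned.

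**The case against.** The strongest reply is that this is a loose phrase in a small observational study: clinical outcomes are undefined, and defining them would cure the fault. The list of clinical data is open-ended, since time on dialysis and comorbidities are given only as examples. Section 3 also refers to other information in hospital records: "All other reviewed tests are those that have already been performed for clinical reasons". Predictor is ordinary regression vocabulary for an independent variable, in cross-sectional work too. Section 9 already commits to transparency about limitations.

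Part of this stands. The list is not strictly closed, so the accurate statement is that no outcome is named and no ascertainment is described. It would go too far to say that none could ever be found in the records. Predictor alone would be a matter of wording. It becomes misleading when coupled with clinical outcomes. A general promise of transparency does not withdraw a specific analysis that the design cannot deliver.

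A reader might infer more than the documents support:

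- **That a study aim fails.** It does not. The phrase occurs in the analysis paragraph of section 8 and not among the objectives in section 5.
- **That past events will be used as outcomes, so reverse causation is certain.** No text says that outcomes will be drawn from records. The sentence in section 3 concerns tests and explains why no extra cost arises. Section 7 also excludes patients with recent acute illness or surgery affecting hydration or nutrition. Uncertain order in time is enough for the point.
- **That one BIA reading per patient is stated.** It is a reasonable inference from the design and the description of the procedure, but the protocol does not say so.
- **That the problem is too few events.** An event count would need mortality or admission rates that the protocol does not give. With no outcome collected, it would add nothing.

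**Conclusion.** The point holds as a fault in one stated secondary analysis. Section 8 commits to a regression on clinical outcomes, while the same section and section 6 describe a cross-sectional study with 0 of 12 listed items named as an outcome and analysis in the month after a two-month collection. The follow-up period in section 9 dates to about April 2025 and does not change this.

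The conclusion rests on two readings: that comorbidities and similar clinical data are characteristics unless the protocol calls them outcomes, and that the cross-sectional label means what it says. It needs no assumed event rates. The fault is worth correcting, because following the sentence yields either no model or an unsupported prognostic claim. It is limited in reach, because the primary BIA-eGFR correlation is untouched.

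**What to change.** In the analysis paragraph of section 8, delete the reference to clinical outcomes and describe what remains as an association analysis, for example: *Regression analysis will estimate cross-sectional associations of phase angle, lean body mass and fluid status with malnutrition.* State in the report that the study supports no prognostic conclusion about BIA or eGFR.

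The cost is a change to one sentence and a narrower secondary claim. No extra patients, visits or tests are needed. Section 9 can stay as it is for this purpose, since its wording on the follow-up period affects only deletion of the code key and changes no result.

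The alternative is to keep the target and define the outcomes, their source and an observation period after the BIA reading. That would be a different design on a longer timeline than section 6 allows, so deletion is the proportionate choice.
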